12.3 Inspection of Records

Neurotrope, Inc., will be allowed to conduct site visits to the investigation facilities for the purpose of monitoring any aspect of the study. The PI agrees to allow the monitor to inspect the drug storage area, study drug stock, drug accountability records, subject charts and study source documents, and other records relative to study conduct.

12.4 Retention of Records

A searchable offline version of the eCRF will be forwarded to the Sponsor for storage. A copy of each completed eCRF will remain in the PI's study file on a compact disk. All source documentation, eCRFs and administrative records will be retained by the PI for a minimum of 2 years following agency approval of the medication for the indication under study or following notification that the investigational application is closed for this indication. However, this may be adjusted based on the applicable local requirements. After this time, the documentation will either be destroyed or transferred to Neurotrope or designee. No study documentation should be destroyed or moved to a new location without prior written approval by Neurotrope.

12.5 Confidentiality

All study findings and documents will be regarded as confidential. The PIs and members of their research teams must not disclose such information without prior written approval from Neurotrope or its representatives.

The anonymity of participating subjects must be maintained. A Protected Health Information statement will be provided to each subject either as a part of the Informed Consent document or as a separate form. Subjects will be identified on eCRFs and other documents by their initials, birth date, and subject number. Documents that identify the subject by name (eg, the signed Informed Consent Form) must be maintained in strict confidence by the PIs.

12.6 Protocol Amendments

Minimally, any change that significantly affects the safety of subjects, the scope of the investigation, or the scientific quality of the study will be effected by means of a protocol amendment approved by the Sponsor. Any changes that affect subject safety or welfare must be submitted to the relevant IRB and approved before implementation.

The PI will provide written agreement of the protocol amendment via the approval signature page. The PI will notify the IRB of the amendment and obtain approval prior to implementation. If the change is intended to eliminate an immediate hazard, the amendment will be implemented immediately, prior to IRB notification.

12.7 Protocol Deviations

Should a deviation from the protocol be deemed crucial for the safety and well-being of a particular subject, such a deviation will be instituted for that subject only. The PI or other attending physician should contact the Medical Monitor as soon as possible. In addition, the PI or designee should document in the source document the reasons for the protocol deviation and the ensuing events. No protocol deviations for any Inclusion or Exclusion criterion will be permitted in this study.

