4.4.2 Exclusion Criteria

1. Dementia due to any condition other than AD, including vascular dementia (Rosen-Modified Hachinski Ischemic score ≥ 5)
2. Evidence of significant central nervous system (CNS) vascular disease on previous neuroimaging including but not limited to: cortical stroke, multiple infarcts, localized single infarcts in the thalamus, angular gyrus, multiple lacunar infarcts or extensive white matter injury
3. Clinically significant neurologic disease or condition other than AD, such as cerebral tumor, chronic subdural fluid collections, Huntington's Disease, Parkinson's Disease, normal pressure hydrocephalus, or any other diagnosis that could interfere with assessment of safety and efficacy
4. Evidence of clinically significant unstable cardiovascular, pulmonary, renal, hepatic, gastrointestinal, neurologic, or metabolic disease within the 6 months prior to enrollment. If there is a history of cancer the subject should be clear of cancer for at least 2 years prior to screening. More recent history of basal cell or squamous cell carcinoma and melanoma in situ (Stage 0) may be acceptable after review by the Medical Monitor.
5. Creatinine clearance (CL) of $<45\text{ml/min}$
6. Poorly controlled diabetes, at the discretion of the Principal Investigator
7. Concomitant treatment with NMDA receptor antagonists such as but not limited to memantine or drug combinations containing memantine, dextromethorphan (a cough suppressant), ketamine, phencyclidine (PCP), methoxetamine (MXE), nitrous oxide (N_2O) and the following synthetic opioids: pentidine, levorphanol, methadone, dextropropoxyphene, tramadol, and ketobemidone.
8. Use of vitamin E > 400 International Units (IU) per day within 14 days prior to screening
9. Use of valproic acid within 14 days prior to screening
10. Use of an active Alzheimer's vaccine within 2 years prior to screening
11. Use of a monoclonal antibody for treatment of AD within 1 year prior to screening
12. Any medical or psychiatric condition that is likely to require initiation of additional medication or surgical intervention during the course of the study

13. Any screening laboratory values outside the reference ranges that are deemed clinically significant by the PI
14. Use of an investigational drug within 30 days prior to screening

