Sites will not be able to randomize subjects before confirmation that eligibility criteria have been met per the review of the Rosen-Modified Hachinski Scale, MMSE-2, CSSRS, and other eligibility criteria by the Worldwide Clinical Trials' Clinical Assessment Technologies (CAT) group and Medical Monitor (MM).

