6.2.2 Week 0 (Day 0 Dose 1)

If the subject has had no intervening medical issues or changes in medications between the date of randomization and Week 0, dosing may proceed as scheduled.

A final assessment of the inclusion/exclusion criteria, including any changes in medications or health status will be done before dosing to confirm the subject's eligibility.

The following procedures will be done on Day 0:

- *Dosing by IV infusion* will be done according to the procedures outlined in Section 5.7.

- Vital signs prior to infusion, then at 30(\pm 5), 60(\pm 5) and 90(\pm 5) minutes from start of the infusion
- AEs and concomitant medications

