6.2.11 Week 15 or End of Treatment Follow-up Visit

For subjects who have completed the study, a follow-up visit will take place at Week 15, 30 days after the last dose of study drug. Subjects who have withdrawn from the study will have a follow-up visit 30 days after the last dose of study drug. The following will be performed:

- SIB
- MMSE-2
- ADCS-ADL-Sev
- Vitals
- AEs and concomitant medications

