6.3.3 Prohibited Medications

Memantine is prohibited. Subjects previously treated with memantine must stop treatment at least 30 days prior to initiation of study drug treatment. Treatment with other NMDA receptor antagonists such as but not limited to dextromethorphan (a cough suppressant), ketamine, phencyclidine (PCP), methoxetamine (MXE), nitrous oxide (N₂O) and the following synthetic opioids: pentidine, levorphanol, methadone, dextropropoxyphene, tramadol, and ketobemidone is prohibited and a 30-day washout period is required prior to initiation of study drug treatment.

High dose Vitamin E (> 400 IU / day), Valproic Acid and divalproex sodium are prohibited.

If the PI determines that initiation of any of the prohibited medications is required to ensure the subject's safety, the medication may be initiated with the notification of the Medical Monitor and proper documentation of a protocol deviation. Other restricted concomitant medications are listed in Appendix 1.

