7.7 Criteria for Withdrawal of Subjects

Subjects may be withdrawn from the clinical study for the following reasons:

- The PI believes withdrawal to be medically necessary or in the best interest of the subject
- Noncompliance with the protocol as judged by the PI (requires discussion with the Sponsor)
- Subjects who are enrolled in violation of inclusion and/or exclusion criteria
- An AE that presents an unacceptable consequence or risk to the subject as judged by the PI, Sponsor or the Medical Monitor
- Lost to follow up
- Withdrawal of consent
- Subject is unblinded

Subjects may voluntarily discontinue their participation in the study at any time without prejudice to further treatment.

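### Protocol 7.7 lets a dosed subject found ineligible be withdrawn from the whole study, and 6.2.11 then leaves no Week 13 SIB for most withdrawal times, although the subject still belongs in the FAS

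*Protocol*

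**What the plan says.** Protocol 7.7 opens its list with "Subjects may be withdrawn from the clinical study for the following reasons", and one entry reads "Subjects who are enrolled in violation of inclusion and/or exclusion criteria". The withdrawal is from the study, not only from study drug, which has its own list in 7.8. The entry has no time limit.

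Protocol 6.2.11 sets what happens next: "Subjects who have withdrawn from the study will have a follow-up visit 30 days after the last dose of study drug". That visit includes the SIB, MMSE-2 and ADCS-ADL-Sev. No section schedules a Week 13 visit for a withdrawn subject.

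Two checks come before dosing. Section 6.2.1 says "Sites will not be able to randomize subjects before confirmation that eligibility criteria have been met", and 6.2.2 says "A final assessment of the inclusion/exclusion criteria, including any changes in medications or health status will be done before dosing".

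Protocol 12.7 adds that "No protocol deviations for any Inclusion or Exclusion criterion will be permitted in this study". It attaches no consequence to a violation discovered later.

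In the SAP, the FAS (6.1) requires a dose and a post-baseline efficacy assessment and has no eligibility condition. The CAS (6.3) requires 12 weeks of treatment and a Week 13 SIB. Missing efficacy values are multiply imputed (7.3.1). The primary endpoint is the change in SIB total score from baseline to Week 13 (2.6.1).

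**The concern.** The analysis population and the follow-up rule do not match. The FAS keeps a dosed subject who turns out to have been ineligible, but 7.7 with 6.2.11 allows collection of that subject's primary endpoint to stop. An observable value is replaced by an imputed one because of a decision taken after randomisation, possibly by someone who knows how the subject has fared. The subject may be willing to continue.

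The protocol takes a different line elsewhere. Under 5.6, after unblinding, study drug stops but efficacy and safety monitoring continues. Nothing equivalent is written for a subject found ineligible.

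At stake are avoidable missing values in the primary endpoint. The SAP names only the CAS as a supportive analysis (8.2), and the CAS drops the same subjects, so it cannot show whether their loss matters.

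**Working it through.** **1. When the 30-day visit falls.** Dose days and the ±2-day visit window come from the Schedule of Activities (Protocol 6.0). The Week 13 window is 91 ± 2, that is Day 89 to 93. Follow-up day = last dose day + 30.

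| Last dose (nominal day) | 30-day visit | Against Day 89 to 93 |
|---|---|---|
| 0 | 30 | before |
| 7 | 37 | before |
| 21 | 51 | before |
| 35 | 65 | before |
| 49 | 79 | before |
| 63 | 93 | last day of window |
| 77 | 107 | after |

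For the first five doses the visit windows do not rescue the endpoint. The latest case is 49 + 2 + 30 + 2 = Day 83, still before Day 89. Only a last dose at Week 9 puts the visit at the edge of the window, and the SAP has no rule for treating such a visit as Week 13. After the seventh dose, the Week 13 SIB is lost if withdrawal comes before Week 13.

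**2. What the analysis does with the subject.** If any post-baseline efficacy assessment exists (Week 5, Week 9 or the 30-day visit itself), the subject is in the FAS with an imputed Week 13 value. Without a Week 13 SIB the subject is not in the CAS.

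**3. The plan's power figures.** Inputs from Protocol 9.0 and SAP 3: SDs 6.8 and 6.7, two-sided alpha 0.05, two-sample t-test, 1:1 allocation.

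- Pooled SD = √((6.8² + 6.7²)/2) = 6.75.
- Noncentrality = difference / (6.75 × √(2/n)), with 2n − 2 degrees of freedom. For 4.5 points and n = 37: 4.5 / (6.75 × 0.2325) = 2.87, giving 80.8% (stated: 80%).
- At n = 50, differences of 4.0, 4.5, 5.0 and 5.5 give 83.5%, 91.0%, 95.6% and 98.1% (stated: 83%, 91%, 95%, 98%).
- At n = 37, differences of 5.0 and 5.5 give 88.2% and 93.3% (stated: 88%, 93%).

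The stated figures reproduce.

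**4. Illustrative cost in power.** The number lost is an assumption, because the documents give none. This is an observed-case t-test; the planned analysis is ANCOVA with multiple imputation, so the figures only indicate scale.

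| Extra losses per arm | From 37 per arm, 4.5 points | From 50 per arm, 4.0 points |
|---|---|---|
| 0 | 80.8% | 83.5% |
| 1 | 79.7% | 82.7% |
| 2 | 78.5% | 82.0% |
| 3 | 77.3% | 81.1% |
| 5 | 74.7% | 79.4% |

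**5. Illustrative bias.** Assume 2 of 37 subjects in one arm are removed, would have changed by 5 to 10 points less favourably than the rest, and are imputed at the mean of the rest. The arm mean is then off by 2 × 5/37 = 0.27 to 2 × 10/37 = 0.54 points, or about 7% to 14% of a 4.0-point effect. All three inputs are assumed.

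**The case against.** The strongest reply is that this will rarely happen. Eligibility is confirmed centrally before randomisation and checked again on Day 0, withdrawal under 7.7 is optional, and SAP 7.3 promises every effort to obtain data from all randomised subjects. The 37 per arm already allows for 25% dropout from any cause. In study NTRP101-202, 113 of 147 randomised subjects (76.9%) had a Week 13 SIB, about 38 of 50. Any loss of this kind may sit inside that allowance. All of this stands and limits the size of the problem. It does not supply the missing Week 13 visit.

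Four stronger readings are tempting, and the documents do not support them.

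- **That 12.7 forces removal.** It bans eligibility deviations and orders no withdrawal. The route is 7.7 with 6.2.11.
- **That a need for new medication after dosing makes a subject ineligible in retrospect.** Exclusion 12, "Any medical or psychiatric condition that is likely to require initiation of additional medication or surgical intervention during the course of the study", most naturally describes a forecast at entry, and 7.7 speaks of subjects enrolled in violation. Protocol 6.3 expects medication changes during the study and asks that they be noted.
- **That 12.7 and 6.3.3 flatly contradict each other.** For a prohibited drug needed for safety, 6.3.3 says "the medication may be initiated with the notification of the Medical Monitor and proper documentation of a protocol deviation". The opening of 12.7 also allows a deviation crucial to one subject's safety. What is unclear is whether the ban on eligibility deviations reaches past entry, since exclusion 7 concerns concomitant treatment.
- **That removals would fall more on bryostatin.** In study NTRP101-202, treatment-related TEAEs affected 37.0% of subjects on 20 µg and 16.7% on placebo (Protocol 2.1.4). These are neither eligibility violations nor withdrawals. The same section gives TEAEs leading to drug discontinuation in 1 subject against 2, and non-fatal SAEs in 2 against 4, which point the other way.

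**Conclusion.** The point holds as a gap between 7.7, 6.2.11 and the FAS definition. A dosed subject found to have been enrolled in violation may be withdrawn from the study, and for five of the seven possible last-dose days the only remaining visit falls before the Week 13 window. The observed value is then lost, imputed in the FAS and absent from the CAS.

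The size is unknown and probably small. No violation rate is given and no unequal effect between arms is shown. One extra loss per arm costs about one point of power at 37 per arm, and 79.7% still rounds to the stated 80%. A reader might infer that the power claim fails or that the effect estimate is biased; neither is established. The case for change rests on the loss being avoidable and judgement-dependent, in the primary endpoint of a trial of 100 subjects, and cheap to prevent.

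**What to change.** - **Protocol 7.7:** remove eligibility violation as a reason for withdrawal from the study once a subject has been dosed.
- **Protocol 7.7 and 6.2.11:** state that such a subject, unless consent is withdrawn, stays in the scheduled efficacy and safety assessments through the Week 13 SIB and is analysed in the FAS as randomised. Whether study drug continues is a separate decision that this text should leave alone. The positive statement is needed in 6.2.11, where the Week 13 visit is lost; deleting the 7.7 entry alone leaves other listed reasons under which the same subject could be withdrawn.
- **Consistency with 5.6:** the wording there on continued monitoring after unblinding is a ready model. Because 7.7 also lists unblinding as a reason for study withdrawal, those two sections should be reconciled in the same edit.
- **Clarification only:** say in 12.7 and 6.3.3 whether the ban on eligibility deviations applies at entry or also to medication changes on study.

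The cost is a few sentences in a protocol amendment, with no new type of visit and no extra subjects. The small downside is that a few ineligible subjects contribute observed rather than imputed data to the FAS, to which they already belong if they have a post-baseline efficacy assessment.

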12.8 Data Corrections

For all written documentation such as source documents, the data collected during the study must be legibly printed using a permanent ink pen. A single line should be drawn through any incorrect information. Opaque correction fluids or tapes are not permitted. All corrections or deletions to any of the source documents must be dated and initialed. All corrections or deletions to the eCRF will be documented via an electronic audit trail. The PI will electronically sign each subject's final eCRF to signify that all of the information is correct and complete.

12.9 Insurance

The Sponsor has taken out a liability insurance policy, which covers the liability of PIs. This policy is in accordance with local laws and requirements.

The Sponsor's insurance does not relieve the PI or the collaborators of any obligation to maintain their own liability insurance policy as required by the applicable law.

13 PUBLICATION AND DISCLOSURE POLICY

Study findings are an integral part of the overall commercialization plan for this investigational compound. To this end, the contents of this protocol and any amendments and results obtained during the study shall be kept confidential by the investigator, the investigator's staff, and the IRB/IEC, and shall not be disclosed in whole or in part to others, or used for any purpose other than reviewing or performing the study, without the review and prior written consent of the Sponsor. These obligations of confidentiality and non-use shall in no way diminish such obligations as set forth in either the Confidentiality Agreement or Clinical Trial Agreement executed between the Sponsor/CRO and the institution/investigator. All persons assisting in the performance of this study must be bound by the obligations of confidentiality and non-use set forth in either the Confidentiality Agreement or Clinical Trial Agreement executed between the institution/investigator and the Sponsor/CRO. Additionally, the publication plan of the Sponsor, considering, among other items, proprietary patent issues and competitive strategic goals, must be complied with prior to the public disclosure of any aspect of this study by abstract, verbal presentation, invited lecture, journal article, or journal letter. Matters regarding authorship and the order of authorship on publications reporting the results of single study findings are covered in a separate agreement.

14 APPENDIX 1 - RESTRICTED CONCOMITANT MEDICATIONS

Drugs Allowed (Y) and Not Allowed (N) as Concomitant medications in this study.

Drug Class	Usage		Restrictions
	(p.r.n.)	Chronic Use	
Analgesics	(Y)	(Y)	
Only non-opioid containing analgesics can be administered chronically.
 
Use of acetaminophen as an analgesic is contraindicated as it has the ability to inhibit PKC activation.
 
Combination products containing codeine, hydrocodone or oxycodone may be used on a p.r.n. basis only (not to exceed 5 consecutive days) and not within 24-hours before a clinic visit.
 
Opioid analgesics are contraindicated as they have the ability to act as an NMDA antagonist.

Anesthetics			

 • General • Local 	(N) (Y)	(N) (N)	
Anorexics	(N)	(N)	
Antacids	(Y)	(Y)	
Antianginal agents	(Y)	(Y)	
Antiarrhythmics	(N)	(Y)	Dose must be stable for 1 month prior to Screening.
Antiasthma agents	(Y)	(Y)	
Antibiotics	(Y)	Call	Call Medical Monitor.
Anticholinergics	(N)	(N)	Includes Cogentin. Anticholinergics for bladder control are to be avoided if possible. When needed some, such as Detrol is allowed. Call Medical Monitor.

Drugs Allowed (Y) and Not Allowed (N) as Concomitant medications in this study.

Drug Class	Usage		Restrictions
	(p.r.n.)	Chronic Use	
Anticoagulants	(N)	(Y)	Heparin is not allowed
Anticonvulsants	(N)	(N)	Divalproex, Valproate, Topiramate are prohibited. Anticonvulsants with no known significant cognitive effects, such as Lamictal, Pregabalin, Levetiracetam are allowed. Call the medical monitor for other anticonvulsants. Patient must have been on a stable dose for 3 months prior to screening.
Antidepressants	(N)	(Y)	MAO inhibitors, antidepressants with anticholinergic effects (e.g. tricyclics), and chronic use of sedating antidepressants (e.g. mirtazipine) are not allowed. Sedating antidepressants can be used sparingly at low dose, as needed for sleep; avoid using 12 hrs prior to efficacy assessments. Dose and medication must be stable for 1 month prior to Screening.
Antidiarrheal preparations	(Y)	(N)	Kaolin, Imodium and Pepto-Bismol preparations are allowed. Call Medical Monitor for others.
Antiemetics	(Y)	(N)	Antiemetics with sedative properties (e.g. first generation antihistaminics) are not allowed. Antiemetics such as phosphoric acid preparations (Emetrol, Emecheck), Pepto-Bismol, and cola syrup are allowed.
Antifungal agents			
• Systemic	(N)	(N)	
• Topical	(Y)	(Y)	
Antihistamines	(Y)	Call	Non-sedating antihistaminics such as Allegra (fexofenadine), Zyrtec (cetirizine) etc are allowed. Sedating antihistaminics are not allowed. See cough and cold

Drugs Allowed (Y) and Not Allowed (N) as Concomitant medications in this study.

Drug Class	Usage		Restrictions
	(p.r.n.)	Chronic Use	
			preparations for combination products.
Antihypertensives	(N)	(Y)	Diupres (reserpine), Catapres (clonidine), Minipress (prazosin), Inderal (propranolol), Wytensin (guanabenz), Tenex (guanfacine) and Aldomet (methyldopa) are not allowed. All others - medication and dose must be stable for 1 months prior to Screening.
Anti-inflammatory drugs	(Y)	(Y)	Indomethacin and systemic corticosteroids are not allowed.
Anti-neoplastics	(N)	(Y)	Tamoxifen is allowed. Dose must be stable for 3 months prior to Screening.
Anti-obesity	(N)	(Y)	Xenical (orlistat) Cetilistat, Lorcaserin (Belviq) are allowed. Others such as Qsymia (a combination of phentermine and topiramate) are not allowed. Call Med Monitor. Dose must be stable for at least one month prior to Screening.
Anti-Parkinson's drugs	(N)	(N)	Includes dopaminergic agents, amantadine, selegiline, Cogentin, and MAO inhibitors.
Antipsychotics	(Y)	(Y)	Clozapine and antipsychotics with anticholinergic effects are not allowed. Limit use to low doses and only if absolutely needed. Call Medical Monitor. Doses must be stable for at least one month prior to Screening.
Antiviral agents	(Y)	(Call)	Zovirax, Valtrex, Famvir are allowed. For others, call Medical Monitor
Anxiolytics	(Y)	(N)	Limited use of short/medium acting benzodiazepines if needed is allowed. Do not use within 12 hrs before efficacy assessments.
BPH agents	(N)	(Y)	Alpha-1 blockers (Hytrin, Flomax, Cardura) and finasteride are

Drugs Allowed (Y) and Not Allowed (N) as Concomitant medications in this study.

Drug Class	Usage		Restrictions
	(p.r.n.)	Chronic Use	
			permitted. Drug and dose must be stable for 3 months prior to Screening.
Cholinesterase inhibitors	(N)	(Y)	Alzheimer's disease medications such as Aricept (donepezil) Exelon (rivastigmine), and Reminyl (galantamine) must be on a stable dose for at least 3 months prior to Screening. Usage must continue unchanged throughout the study.
Cough/Cold preparations	(Y)	Call	Decongestants containing dextromethorphan or narcotics are not permitted. Preparations containing pseudoephedrine or phenylpropanolamine are not permitted. See Antihistamines.
Diuretics	(N)	(Y)	Medication and dose must be stable for 1 months prior to Screening.
Ginko biloba	(N)	(Y)	Dose must be stable for at least one month prior to Screening.
H ₂ Blockers	(Y)	(Y)	For patients on chronic therapy, medication and dose must be stable for 1 months prior to Screening.
Hormones	(N)	(Y)	Medication and dose must be stable for 3 months prior to Screening.
Hormone suppressants	(N)	(Y)	Proscar (finasteride) is allowed. Dose must be stable for 3 months prior to Screening.
Hypoglycemic agents	(N)	(Y)	Oral hypoglycemic agents and insulin are allowed. Dose must be stable for 3 months prior to Screening.
Hypolipidemics	(N)	(Y)	Statins are allowed. Dose must be stable for at least one month prior to Screening.
Insulin	(N)	(Y)	Patients must be well controlled and stable.
Laxatives	(Y)	(Y)	Fiber-based products and Colace

Drugs Allowed (Y) and Not Allowed (N) as Concomitant medications in this study.

Drug Class	Usage		Restrictions
	(p.r.n.)	Chronic Use	
			(docusate sodium) are allowed.
Muscle relaxants	(N)	(N)	
Psychotropic drugs not otherwise specified (including herbal products)	(N)	(N)	Call medical monitor
Sedatives/hypnotics	(Y)	(Y)	Zolpidem, zaleplon, trazodone, chloral hydrate, mirtazapine, and the occasional use of benzodiazepines for sleep is allowed. Where possible, these should not be used within 12 hrs prior to efficacy tests.
Steroids			
• Systemic	(N)	(N)	
• Topical	(Y)	(Y)	
• Inhalant	(Y)	(Y)	
Stimulants	(N)	(N)	Includes Ritalin, Concerta, any methylphenidate preparations, Cylert (pemoline), etc.
Tocopherol (Vitamin E)	(N)	(Y)	Dose more than 400 IU per day not allowed; Dose must be stable for at least one month prior to Screening.
Vaccines for AD	N	N	Patients treated with active vaccine against amyloid/tau within 2 years are not allowed.

